1. OBJECTIVES

This project will be subdivided into three sections:

Part I. Comparison of the ESM vs. SR-BDs and other retrospective questionnaires in the assessment of urological complaints in OAB such as urgency.

Part II. Validation of new patient-reported outcome measure, based on the Experience Sampling Method, which will be used in the assessment of urological symptoms in patients with overactive bladder syndrome.

Part I – Comparison of assessment methods

Primary aim: To compare the ESM to SR-BDs and other retrospective questionnaires in the assessment of urological complaints in OAB.

Objectives:

1. To compare the ESM to SR-BDs and other retrospective questionnaires in the assessment of urological complaints in OAB.

Hypothesis: The ESM is more accurate in the assessment of urological complaints in OAB compared to the current use of SR-BDs and other retrospective questionnaires (like the OAB-q). We hypothesize to find good correlations between ESM scores (i.e. the newly developed ePRO) and 'concurrent' instruments (i.e. conventional retrospective questionnaires), since we purport to measure the same constructs with both methods. However, ESM measures real-time symptoms whereas our conventional questionnaires measure retrospectively. Therefore, we do not expect to find perfect correlation coefficients, i.e. >0.8. Correlation coefficients between 0.4 and 0.8 are considered appropriate. Correlation coefficients lower than 0.4 reflect very weak or no correlation between the methods, which probably means that we are measuring some other construct with our new ePRO than is measured with the conventional method (current 'gold standard'). On the contrary, correlation coefficients higher than 0.8 reflect very strong correlations, meaning that we are more or less measuring exactly the same construct. In this case, there is no rational for replacing the conventional methods by the new (more intensive) method. For each correlation coefficient its significance will be checked as well.

Furthermore it is expected that the mean urgency scores from the ESM will be significantly lower when compared to the urgency scores from the SR-BDs and retrospective questionnaires.

Additionally it is expected that in the SR-BDs the daily peak of urgency scores is reported rather than the average level of urgency over the day.

Part II - Validation

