Primary aim: To validate and test the reliability of electronic patient-reported outcome (ePRO) for the evaluation of the complex symptoms and their potential triggers in OAB patients in day-to-day life with the use of the Experience Sampling Method.

Objectives:

1. To assess content validity of the developed ePRO.

Hypothesis: We consider content validity of the ePRO adequate since items were carefully selected based on evidence from qualitative studies. Furthermore, item relevance was judged by a multidisciplinary panel of experts in the fields of urology, gastro-enterology, psychiatry and gynaecology as well as by OAB patients.

2. To assess concurrent validity of the developed ePRO.

Hypothesis: We hypothesize to find good correlations between ESM scores (*i.e.* the newly developed ePRO) and 'concurrent' instruments (*i.e.* conventional retrospective questionnaires), since we purport to measure the same constructs with both methods. However, ESM measures real-time symptoms whereas our conventional questionnaires measure retrospectively. Therefore, we do not expect to find perfect correlation coefficients, *i.e.* >0.8. Correlation coefficients between 0.4 and 0.8 are considered appropriate. Correlation coefficients lower than 0.4 reflect very weak or no correlation between the methods, which probably means that we are measuring some other construct with our new ePRO than is measured with the conventional method (current 'gold standard'). On the contrary, correlation coefficients higher than 0.8 reflect very strong correlations, meaning that we are more or less measuring exactly the same construct. In this case, there is no rational for replacing the conventional methods by the new (more intensive) method. For each correlation coefficient its significance will be checked as well.

3. To assess internal consistency of the developed ePRO.

Hypothesis: We hypothesize that internal consistency of the ePRO will be moderate to good, since items were based on theoretical constructs as described in literature. Therefore, we expect to find correlation coefficients (Cronbach's α) of >0.6.

4. To assess test-retest reliability of the developed ePRO.

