3.4 Sample size calculation

The outcome of the ESM is multidimensional; it gives information about the (urological) complaints but also the context in which the complaints arise. An inter-individual analysis can be made with the use of ESM, and because of this extensive data can be collected per patient.

An appropriate sample size can therefore not be made.

In previous literature the sample size differs from N=5 ²⁷, N= 10 ³⁸, N = 19 ³⁹, N= 26 ¹ to N=40 ⁴⁰. In the study of Cabrita et. al. random slopes could not be included in the multilevel regression analysis because of the sample size being too small to validly estimate all associated parameters, but an individual analysis with linear regression models with random intercept has been made.³⁸ Other studies using ESM in a population between 19 to 40 patients have shown that clinically relevant differences could be detected using an alpha of 0.05.^{1,39-41} However, epidemiologic literature suggest that as a rule-of-thumb, a sample of at least N = 50 is required to evaluate construct validity^{42,43} and to recognize a factor pattern.⁴⁴ Therefore, we need to include at least 50 participants.

Empirical studies using ESM showed that about 5% to 23.2% of the patients did not comply (defined as completing the ESM questionnaire in less than 50% of the beeps).^{1,27,38-41} Taking into account a conservative non-valid ESM data rate of 23%, a sample size of 66 patients is needed to obtain 50 ESM questionnaires that can be used for the analysis.

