- Internal consistency is a reliability measure to analyse correlations between single items of an instrument/scale that are supposed to measure similar symptoms or domains. The homogeneity of a scale (*e.g.* internal consistency) is analysed by Cronbach's α-statistic. A coefficient of at least 0.6 is generally considered as acceptable, values above 0.8 are considered as good to very good ^{29,64-66}. As subjects are usually not able to respond after every beep (for example because of driving a car), completion of ≥6 of the 10 beep-questionnaires per day will be considered as being compliant. Not completed beep-questionnaires will be considered as missing values in the analyses.^{1,67}
- Test-retest reliability reflects the consistency between repeated measurements of the same outcome in the same test conditions, but at different times. We will ascertain on individual response consistency over the study period. Scores of the first half-week will be correlated with scores of the second half-week. A test-retest reliability coefficient of more than 0.70 will be considered adequate ²⁹.
- Differences between OAB symptom scores assessed by the OAB-q / ICIQ-FLUTS / IPSS and ESM could only be analysed on subject level, by paired sample t-test, due to lack of intra-subject variation in the OAB-q scores (only one measurement per subject). Scoring scales of the retrospective questionnaires and ESM will be harmonized by rescaling the ESM data from a 11-point to a 6-point and 5-point scale. In order to assess whether the rescaling affected the reliability of urological symptom related questions in ESM, a Cronbach's a was calculated for the original and rescaled data. Subject-means (i.e. means over 7 days) of ESM data were calculated and compared to the corresponding OABg / ICIQ-FLUTS /IPSS scores.
- Following the COSMIN guidelines it should be aimed to assess the responsiveness of the ESM tool too. However, since responsiveness is the sensitivity of an instrument to detect difference between two points in time within groups⁶⁸, this psychometric property, it is not meaningful to assess this, since the ESM measures repeatedly over a longer period of time (10 times a day for 7 days). It is expected that there will be a fluctuation of symptoms during the assessment period, however 'big' differences that could be assessed with statistical analysis are not expected to occur. The

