aim of this study is not to detect change between two groups with the use of statistical analysis. It is rather to evaluate symptom pattern recognition of the ESM tool. Therefore responsiveness will not be assessed as psychometric property in this study.

A significance level (α) of 0.05 will be considered statistically significant. Data analysis will be performed using IBM SPSS Statistics software version 23.0 (IBM Statistics for Windows, Armonk, New York).

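### The 0.4, 0.8 and 0.70 verdicts on validity and test-retest reliability rest on point estimates alone, and the planned significance check does not bear on those cut-offs

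*Combined protocol and SAP*

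**What the plan says.** Section 1 (Objectives) states the same rule under Part I, objective 1 and Part II, objective 2. A coefficient below 0.4 is read as little or no correlation and probably a different construct. For the middle range, "Correlation coefficients between 0.4 and 0.8 are considered appropriate". Above 0.8 the two methods are taken to measure the same thing, and the plan then sees no reason to replace the conventional methods. The rule closes with "For each correlation coefficient its significance will be checked as well".

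Section 6.1 sets the reliability criterion, "A test-retest reliability coefficient of more than 0.70 will be considered adequate", and mentions no test for it. The same section fixes the level: "A significance level (α) of 0.05 will be considered statistically significant".

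Section 3.4 bases the sample size on a rule of thumb, "a sample of at least N = 50 is required to evaluate construct validity", and concludes that "a sample size of 66 patients is needed to obtain 50 ESM questionnaires that can be used for the analysis". It calculates neither power nor precision. No section gives a confidence interval for any coefficient, or a test of a coefficient against 0.4, 0.8 or 0.70. The other tests in section 6.1 (delta score against zero, paired t-test) concern mean differences.

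**The concern.** The Summary names the psychometric properties of the instrument as the main study outcome, so these cut-offs carry the study's principal conclusions. A significance check normally asks whether a correlation differs from zero. The plan's questions are different: is the correlation at least 0.4, is it above 0.8, does reliability exceed 0.70? If the sampling error is as wide as the bands, an estimate can fall on the wrong side of a cut-off by chance, and nothing planned would show this to the reader. A small p-value beside such a coefficient could even look like support for the verdict.

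**Working it through.** **Inputs.** Alpha 0.05 (section 6.1; sidedness not stated, two-sided assumed). Evaluable patients 50 of 66, with 23% non-valid data (section 3.4). Patients recruited per sex 33 (section 3.1). Cut-offs 0.4 and 0.8 (section 1) and 0.70 (section 6.1). My assumptions are a null value of zero, a Pearson-type coefficient and one independent pair per patient.

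**The plan's own figure.** 50/(1 − 0.23) = 64.9, so 65 against the stated 66. By sex, 25/0.77 = 32.5, rounded up to 33, and 2 × 33 = 66. The figure is reproduced, and 25 evaluable per sex is the matching lower case for the sex-specific questionnaires.

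**Smallest significant r.** r = t/√(n − 2 + t²), with t the 97.5% point on n − 2 degrees of freedom. For n = 50, t = 2.011 and r = 2.011/√(48 + 4.04) = 0.279. For other n:

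| n | Smallest significant r (two-sided) |
|---|---|
| 25 | 0.396 |
| 33 | 0.344 |
| 50 | 0.279 |
| 66 | 0.242 |

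All lie below 0.4, so any estimate in the 0.4 to 0.8 band or above is significant automatically. One-sided, the values for 50 and 66 are 0.235 and 0.204.

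**Confidence intervals.** tanh(atanh(r) ± 1.96/√(n − 3)). At n = 50 the standard error is 1/√47 = 0.146 and the half-width on the z scale is 0.286.
- r = 0.40: z = 0.424, limits 0.138 and 0.710, so 0.14 to 0.61
- r = 0.60: 0.39 to 0.75
- r = 0.75: 0.60 to 0.85
- r = 0.80: 0.67 to 0.88

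**Chance that the estimate passes a cut-off c when the true value is ρ.** 1 − Φ[(atanh c − atanh ρ)·√(n − 3)]. For ρ = 0.30, c = 0.4, n = 50: (0.424 − 0.310)/0.146 = 0.78, giving 0.217.

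| True value | Verdict from the estimate | n = 25 | n = 33 | n = 50 | n = 66 |
|---|---|---|---|---|---|
| 0.30 | above 0.4 | 0.30 | 0.27 | 0.22 | 0.18 |
| 0.75 | above 0.8 | 0.28 | 0.25 | 0.19 | 0.16 |
| 0.65 (test-retest) | above 0.70 | – | – | 0.26 | 0.23 |

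**Several days per patient.** The bladder diary covers three days, and sections 6 and 6.1 analyse it in a mixed model without saying how a correlation comes out of it. As a favourable extreme, treat 50 × 3 = 150 pairs as independent. The smallest significant r is then 0.16, the interval for r = 0.40 is 0.26 to 0.53, and a true 0.30 exceeds 0.4 about 8% of the time. Correlation within patients puts the real position between this and the n = 50 figures. Single-time questionnaires and the half-week comparison give one pair per patient, so the extreme does not apply to them.

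**Where a verdict would be uncertain at n = 50.** The interval includes 0.4 for estimates from about 0.14 to 0.61, 0.8 for estimates from 0.67 to 0.88, and 0.70 for estimates from 0.52 to 0.82.

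**The case against.** The strongest reply is that the significance check cannot produce a wrong verdict. It is made in addition to the bands, so an r of 0.28 is still classed as little or no correlation whatever its p-value. A reader might infer that the plan would accept 0.28 as evidence of validity. The documents do not support that, and this objection stands in full. The plan also never names zero as the null; that is only the ordinary meaning of a significance check.

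Second, n = 50 with one pair per patient is not the only case. Sex-specific questionnaires have 25 to 33 patients, the diary comparison uses repeated days, and section 4.4 lets drop-outs contribute to Part I and test-retest. This stands as a limit on the figures. It does not remove the problem: with one pair per patient the chance that a true 0.30 is classed as appropriate is 18 to 30%.

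Third, the check is not stated for test-retest, so criticism of a test against zero does not reach 0.70. That is right. What applies there is the absence of any statement of uncertainty.

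Fourth, the bands appear under hypotheses and are worded with some caution, and comparing an estimate with a conventional cut-off is common practice. A reader might infer that the lower confidence limit ought to clear the cut-off. At n = 50 that needs an observed r of about 0.61 for 0.4 and 0.82 for 0.70. The latter is above the 0.70 to 0.80 that the plan expects, and a true test-retest value of 0.75 would pass about 11% of the time. Nothing in the documents calls for so strict a rule, and it would usually block a positive conclusion.

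**Conclusion.** The concern holds in a limited form. The verdicts at 0.4, 0.8 and 0.70 are drawn from point estimates with no allowance for sampling error, and the one planned inferential step does not address those cut-offs. It is uninformative for them, not misleading by design. At 50 evaluable patients the 95% interval spans roughly 0.25 to 0.47 on the correlation scale for the values examined (0.60 to 0.85 for r = 0.75; 0.14 to 0.61 for r = 0.40), against a band 0.4 wide. Chances of a wrong verdict of about 19 to 26% occur for true values 0.05 to 0.10 from a cut-off. These sizes assume a two-sided 5% level, a Pearson-type coefficient and one independent pair per patient. They are larger for sex-specific questionnaires and smaller where repeated days add information. This is an inexpensive improvement in how the main results are reported, not a flaw that invalidates the design.

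**What to change.** In section 1 (Part I, objective 1 and Part II, objective 2), replace the significance check by a 95% confidence interval for each coefficient. In section 6.1, add the same for the test-retest coefficient. Where patients contribute several days, state how the correlation is obtained and use an interval that respects clustering, for example a bootstrap that resamples patients.

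Keep the planned cut-offs on the estimate, including the stated consequence above 0.8. Add one sentence: a verdict whose 95% interval includes the relevant cut-off is reported as uncertain, not as established. Do not require the lower limit to exceed 0.4 or 0.70.

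The cost is wording and a small amount of programming; no patients, visits or data are added. The downside is that many verdicts will be qualified at this sample size. With 50 patients, every test-retest estimate in the hypothesised range of 0.70 to 0.80 would carry the qualifier, and among concurrent-validity estimates within the 0.4 to 0.8 band only those from about 0.61 to 0.67 would be free of it.

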2. STUDY DESIGN

Focus group research in OAB patients was previously done for item selection and to evaluate the quality of the PROMs according to the ESM principle (METC 16-4-189). The outcomes of the focus groups have been discussed in an expert meeting and a final questionnaire has been constructed, specifically for the ESM in the urological patient population. Now, this OAB-specific ESM tool should be tested to see if there is a difference between symptom scores on ESM and the currently used retrospective reports and SR-BDs. The ESM study is a multi-centre, prospective, cross-sectional study in Maastricht UMC+, Zuyderland Heerlen/Sittard and University Hospital Antwerp.

OAB patients will be recruited at the outpatient Pelvic Care Centre at Maastricht UMC+, the outpatient clinic Urology at Zuyderland Heerlen/Sittard and the outpatient clinic Urology at University Hospital Antwerp. Eligible patients are patients that are referred to the urologist by their general physician, other medical specialists or other hospitals with a differential diagnosis of OAB or urinary urgency incontinence. Presently, all new patients that are seen in the outpatient clinic Urology in the MUMC+, the outpatient clinic Urology at Zuyderland Heerlen/Sittard and the outpatient clinic Urology at University Hospital Antwerp are triaged by the staff members of the urology department following the standard of care on the basis of the guidelines for urinary urgency incontinence receive SR-BDs and a HADS questionnaire by post, together with the information about the date of the outpatient clinic appointment in an information package sent by the outpatient nurse. They are asked to fill these out and take these with them for their first urologist appointment.

urologist visit, patients will receive a recruitment letter within the information package to inform them about the study (see 'E3. Wervingstekst_ESM_Urologie_Versie 2.0 (27.10.2017)'). They will also receive written information (see 'E1. Proefpersoon informatie_ESM studie Versie 2.0(18.10.2017)') about the purpose of the ESM study in this information package. During the study, patients have to fill out a lot of questionnaires and repeated assessment of the ESM app. By contacting them prior to the first urology visit, there is no any additional burden of filling out an extra SR-BD (and HADS) for study purposes solely. Patients are asked to contact the coordinating investigator by email or telephone in case of interest in participation. If this is the case, the first visit will be scheduled with one week respite at the medical centre to sign the informed consent form (by the participant as well as the researcher) and to instruct the participant about the study procedures. No study procedures will be performed until the informed consent form is signed. After signing the informed consent form they will receive the login codes of the ESM app and the additional

(retrospective) questionnaires. This way of inclusion ensures that patients are not entrusted with filling out an extra SR-BD for study purposes solely, since they already need to fill these out following the standard of care for their regular scheduled visit.

Healthy volunteers will be recruited by advertisements on bulletin boards at Maastricht University Medical Centre, other public bulletin board in Maastricht and on the website 'www.digiprik.nl' (see 'E3. Advertentie gezonde controles_ESM_Versie 2.0 (18.10.2017)'). Persons that are interested in participating after reading an advertisement are asked to contact the coordinating investigator via email and will then receive the written patient information letter and informed consent form E1. Proefpersoon informatie_ESM studie_Vrijwilligers Versie 2.0(18.10.2017) and E2. IC_ESM_Versie 2.0 (18.10.2017)). One week after receiving this information, a telephone call will follow to answer any additional questions and to verify whether or not the subject is still interested in participating. If this is the case, the first visit will be scheduled at the medical centre to sign the informed consent form (by the participant as well as the researcher), receive the ESM login codes and additional retrospective questionnaires, and to instruct the participant about the study procedures. No study procedures will be performed until the informed consent form is signed.

Study participation will comprise two appointments with the coordinating researcher. During the first visit written informed consent will be obtained and instructions about the study procedures (*i.e.* ESM and retrospective questionnaires) will be given. Hereafter, the participant will complete ESM and the SR-BD during the following week. At the end of the study, the single-time symptom questionnaires will be completed. At the end of this week another appointment ('last visit') follows during which a debriefing session concerning ESM will take place. In the case of included new patients, this appointment directly takes place after the patient is seen by the urologist for their regular outpatient visit. At that moment, all data are collected and study participation is completed. A timeline of the study period is given in **figure 1**.

Figure 1: Timeline of study participation period.

3. STUDY POPULATION

3.1 Population

Thirty-three male and thirty-three female OAB patients will be recruited at the outpatient Pelvic Care Centre in Maastricht UMC+ the outpatient clinic Urology at Zuyderland Heerlen/Sittard and the outpatient clinic Urology at University Hospital Antwerp. Patients will be diagnosed with OAB by their urologist using the ICS criteria for OAB⁵.

Furthermore, thirty-five male and thirty-five female healthy volunteers will be included in order to exploratively evaluate the ability of ESM to discriminate between OAB patients and healthy controls, in terms of triggers for the occurrence and/or persistence of urological symptoms. This control group will be sex- and age-matched to the group of OAB patients.

3.2 Inclusion criteria

3.2.1 Inclusion criteria OAB patients

Patients between 18-70 years with either subjectively experienced OAB for which they have sought medical help or have been diagnosed with OAB by a medical physician. Participants need to be able to understand written Dutch and speak the Dutch language, since the ESM app will be conducted in Dutch. They also have to understand how to practice the ESM tool.

3.2.2 Inclusion criteria healthy volunteers

- Age between 18 and 70 years;
- Male and female
- Ability to understand and speak Dutch;
- Ability to understand how to utilize the ESM tool.

